## 10.5 Primary Analysis

The primary analysis will be conducted on the full analysis set using the same statistical models that were used in the analyses in the pivotal trial. The primary goal of the post approval study is to demonstrate superiority of the Agili-C™ device relative to SSOC at Month 60 by testing the hypothesis:

$$H_0 : \theta_1 = \theta_0 \text{ vs. } H_A : \theta_1 > \theta_0.$$

Where  $\theta_1$  and  $\theta_0$  are the mean improvements in KOOS Overall score from baseline to Month 60 for Agili-C™ and SSOC subjects, respectively. To test this hypothesis, the posterior probability of superiority:  $Pr(\theta_1 > \theta_0 | \text{Data})$  will be evaluated. The post approval study will have met its primary objective if the posterior probability exceeds 0.975 at the final analysis.

As noted above, subjects with ‘treatment failure’ have subsequent outcome values set to their baseline value. The analysis plan specifies that subjects with otherwise missing values are to have their missing values imputed through the Bayesian model. Month 60 imputations are informed by observed data at earlier time points. Non-informative priors distributions are used in all analyses. The SAS procedure PROC BGLIMM (SAS Institute) will be used to determine the posterior probability that Agili-C™ is superior to SSOC in terms of mean changes from baseline to Month 60 in KOOS Overall Score. The BGLIMM procedure is a sampling-based procedure that provides Bayesian inference for generalized linear mixed models (GLMMs). GLMMs are hierarchical models that combine a generalized linear model with normally distributed random effects. The “Bayesian approach estimates the joint posterior distribution of all parameters in a model, including all fixed- and random-effects parameters. The Monte Carlo method numerically integrates out the random effects and propagates the uncertainties to the marginal posterior of the fixed-effects parameters. PROC BGLIMM uses efficient Markov chain Monte Carlo (MCMC) sampling tools to estimate the posterior marginal distributions and use them for further inference” (SAS® 9.4 Help and Documentation ).

CLN0021-US-Investigational Plan		Document Number: CLN-0000002
 CartiHeal		Document Version: 8.0 Effective Date: 08-Jun-2022 (GMT+2) Page 50 of 80
A Post Approval Multicenter Open-label Randomized Controlled Trial of Agili-C™ vs. Surgical Standard of Care (SSOC) for the Treatment of Joint Surface Lesions of the Knee		
		CLN0021-US Rev. 8 March 29, 2022

Therefore, the statistical model used to determine the posterior probability of superiority is the Bayesian analogue to a Mixed Model for Repeated Measures (MMRM). The priors on the fixed effects are very diffuse normal distributions. The prior on the covariance matrix was made minimally informative by setting the degrees-of-parameter to a small value (0.5) and by setting the scale parameter to a relatively large value similar in magnitude to the variances observed for KOOS Overall Score changes. The *Statistical Analysis Report, Version 1.2, September 22, 2021* includes example SAS code for this analysis.

The pivotal trial SAP, Section 9.5.2 specified that analyses of secondary endpoints will be done by “performing a repeated measures analysis using a mixed effects model with terms for treatment, visit, and treatment-by-visit interaction.” As was done for the pivotal trial, for comparison purposes, MMRM will also be applied to the primary endpoint and continuous confirmatory endpoints as well as in covariate analyses designed to evaluate whether relative effectiveness varies among relevant subgroups. To provide meaningful within-group estimates from the Bayesian analysis, the values of the baseline score included as a covariate in the model will be mean centered based on the same analysis data set that served as input (i.e., FAS or PP as appropriate). This results in a within-group estimate at the mean value of the baseline covariate, which is also consistent with how SAS Proc Mixed constructs within group estimates for MMRM.

Two classes of subjects have their 24, 36, 48 & 60 month scores imputed. First, treatment failures (defined in section 12.3) have all scores subsequent to treatment failure imputed to the be their baseline values prior to the analysis. Missing data for subjects lost-to-follow-up are either implicitly imputed using maximum likelihood methods or sampling-based methods or through the use of multiple imputation. The MMRM will utilize an unstructured covariance matrix which allows variances and covariances to vary over time.

	CLN0021-US-Investigational Plan A Post Approval Multicenter Open-label Randomized Controlled Trial of Agili-C™ vs. Surgical Standard of Care (SSOC) for the Treatment of Joint Surface Lesions of the Knee	Document Number: CLN-0000002 Document Version: 8.0 Effective Date: 08-Jun-2022 (GMT+2) Page 51 of 80 CLN0021-US Rev. 8 March 29, 2022
--	--	---

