## 5.11 Number of Centers, Randomization and Allocation

Number of Centers participating: 22.

The subjects in the study will be randomized by site using variable block sizes.

The subjects in the study will stratified by extent of osteoarthritis, defined dichotomously by the Kellgren-Lawrence grade:

- Strata I: 0 & 1
- Strata II: 2 & 3

The study will recruit subjects in US and OUS sites.

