### **7.3.2 Final Screening/Procedure Visit (Visit 2)**

- Between 1 to 90 days after initial screening, subjects will undergo Final Screening (Visit 2) via arthroscopy. If found eligible, the subject will be enrolled into the study and randomized intra-operatively into either Agili-C™ or SSOC. Stratification will be performed based on K/L score performed off-site.
- For the SSOC group, lesion treatment will be determined according to subject's age, lesion size and K/L grade (Table 1) as per the control group selection algorithm (Figure 3).

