## **10.0 Statistical Considerations**

### **10.1 Design Considerations**

This is a two-arm, post approval, open-label, randomized, multi-center study in which subjects are assigned to treatment (Agili-C™) or control (SSOC) in a 2:1 ratio.

The subjects in the study were randomized by site using variable block sizes.

A Post Approval Multicenter Open-label

Randomized Controlled Trial of Agili-C™ vs.

Surgical Standard of Care (SSOC) for the  
Treatment of Joint Surface Lesions of the Knee

CLN0021-US

Rev. 8

March 29, 2022

The subjects in the study will be stratified by extent of osteoarthritis, defined dichotomously by the Kellgren–Lawrence grade:

- Strata I: 0 & 1
- Strata II: 2 & 3

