9.3 Primary Analysis

The primary analysis will be conducted on the FAS population. Complete analysis details may be found in the Adaptive Design Report in Appendix 1.

In addition to the primary Bayesian analysis, the data will be listed and summarized with descriptive statistics by arm.

The primary analysis will be repeated on the PP population.

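### The protocol stratifies randomisation by K/L grade, but Section 10.5 does not name K/L as a term in the Month 60 primary model; if it is absent, adding it is a small, nearly free precision gain

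*Protocol*

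**What the plan says.** **Randomisation.** Protocol 10.1 states: "The subjects in the study were randomized by site using variable block sizes". The synopsis and Sections 5.11 and 10.1 add stratification by K/L grade, 0-1 against 2-3, and Section 7.3.2 says how it is done: "Stratification will be performed based on K/L score performed off-site". SAP Section 6 describes 2:1 randomisation by site in blocks of 3 and 6 and does not mention K/L.

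**Month 60 primary model.** Protocol 10.5 runs the primary analysis on the full analysis set "using the same statistical models that were used in the analyses in the pivotal trial". It describes a Bayesian analogue of an MMRM, fitted in PROC BGLIMM and judged against a posterior probability of 0.975. Two statements bear on its terms:

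- On covariates, "the values of the baseline score included as a covariate in the model will be mean centered".
- From the pivotal SAP's section on secondary endpoints, 10.5 quotes "performing a repeated measures analysis using a mixed effects model with terms for treatment, visit, and treatment-by-visit interaction". That MMRM is also to be applied to the primary endpoint, for comparison.

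Neither statement mentions K/L. For full detail, 10.5 points to a Statistical Analysis Report that "includes example SAS code for this analysis", and SAP 9.3 says: "Complete analysis details may be found in the Adaptive Design Report in Appendix 1".

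**Where K/L does appear.** It defines subgroup endpoints (Protocol 10.7.4, SAP 9.5.3) and enters one-covariate-at-a-time MMRMs aimed at the treatment-by-covariate interaction (Protocol 10.9, SAP 9.7). None of these is the analysis to which the 0.975 rule applies.

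**The concern.** A factor used to balance the arms is normally carried into the primary model. Stratifying removes chance imbalance in that factor from the treatment comparison. A model that ignores the factor still counts its variation as residual noise, so the reported interval is wider than the design warrants. If K/L grade predicts change in KOOS, as osteoarthritis severity plausibly does, the Month 60 posterior interval would be somewhat too wide and the chance of crossing 0.975 somewhat too low. Precision is what is at stake, not the validity of a superiority finding.

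**Working it through.** **Inputs.** From Protocol 10.7.1: one-sided 0.025 pooled t-test, SD 25, n = 120 and 59, differences of 22.5 (as seen at Month 24), 13.9 (reduced case) and 11.2 (smallest difference with 80% power). The share of variance that K/L explains (R²) is not in either document; 1%, 5% and 10% are assumed.

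**Step 1: reproduce the plan's figures.** SE = 25 × √(1/120 + 1/59) = 3.975. Noncentral-t power on 177 df is 99.99% at 22.5 (plan: 99%), 93.55% at 13.9 (plan: 93.5%) and 80.0% at 11.2 (plan: at least 80%). The figures reproduce.

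**Step 2: add a factor with given R².** SE = 25 × √(1 − R²) × √(1/120 + 1/59); half-width = 1.96 × SE.

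| R² | SE | 95% half-width | Power at 11.2 | Power at 13.9 | Power at 22.5 |
|---|---|---|---|---|---|
| 0 | 3.975 | 7.79 | 80.0% | 93.5% | >99.9% |
| 1% | 3.955 | 7.75 | 80.4% | 93.8% | >99.9% |
| 5% | 3.874 | 7.59 | 82.0% | 94.6% | >99.9% |
| 10% | 3.771 | 7.39 | 84.0% | 95.6% | >99.9% |

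The SE falls by 0.5%, 2.5% and 5.1%. The gain is 0.2-2 points at 13.9 and 0.4-4 points at 11.2.

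**Step 3: a model closer to the planned one.** Simulation, 2000 runs per scenario, with the same random numbers for both models. Design: 251 randomised 2:1 in blocks of 3 and 6 within 22 uneven sites × 2 K/L strata (half of subjects assumed K/L 2-3), 239 analysed, 25% lost between Months 24 and 60. Outcome: change at seven visits, total SD 25, baseline explaining 10% of variance, residual correlation 0.5 + 0.5·exp(−lag/12 months). Fit: generalised least squares with known covariance, with visit, treatment-by-visit and baseline-by-visit, with or without K/L-by-visit. The table shows the result without → with K/L.

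| K/L R² | Mean SE | SE reduction | Half-width | Power at 13.9 |
|---|---|---|---|---|
| 1% | 3.563 → 3.549 | 0.4% | 6.98 → 6.96 | 97.40% → 97.60% |
| 5% | 3.552 → 3.469 | 2.3% | 6.96 → 6.80 | 97.70% → 97.95% |
| 10% | 3.537 → 3.365 | 4.9% | 6.93 → 6.60 | 97.85% → 98.50% |

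Power at 22.5 is 100% in every cell. The gain at 13.9 is 0.20, 0.25 and 0.65 points; the first is only 4 of 2000 runs. The starting power exceeds 93.5% because the model uses baseline and the earlier visits of subjects lost later, in line with the remark in Protocol 10.7.1 that its t-test figures are conservative.

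**Step 4: is omission harmful?** Type I error without the term was 1.65-2.15% across the main scenarios (nominal 2.5%, Monte Carlo SE 0.35 points). A separate single-visit simulation gave 1.7-2.4%. There is no inflation.

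**Step 5: cost if the factor does not matter.** K/L-by-visit moves the mean SE from 3.566 to 3.569, under 0.1%. Fixed site terms are less benign. In the repeated-measures model, adding 21 of them gives 3.601/3.569 = 1.009, a 0.9% rise. In the single-visit simulation the SE goes from 3.97 with K/L alone to 4.09 with fixed sites as well, about 3%.

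**The case against.** The strongest objection is that no error is demonstrated. Section 10.5 adopts the pivotal models wholesale, their full specification is in reports not available here, and K/L may already be in them. The list of treatment, visit and treatment-by-visit comes from a secondary-endpoint model, and baseline score is mentioned only to explain centring. Neither is offered as a complete list, so silence about K/L proves little. This stands, and it is why the point is conditional. A reader might infer that the primary model definitely ignores the stratification; the documents do not support that.

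A reader might also infer that leaving out a stratification factor undermines the superiority test. It does not: Step 4 shows an error rate at or below nominal.

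Nor do the documents support insisting that site be added because randomisation was by site. Fixed site terms can raise the SE by 1-3% when sites do not matter. A random site effect needs a prior that 10.5 does not give, in a section that says all analyses use non-informative priors. SAP 9.10-9.11 treat site through poolability tests and a conditional random-effects sensitivity model, though for the 24-month trial.

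Two further objections have force. SAP Section 6 does not list K/L, so the premise itself needs confirming. And changing a primary model in an open-label study with Month 24 results known invites the charge of a data-driven choice, for a gain below one power point at 13.9 in the closer model. These argue for tight conditions on the change. They do not remove the case for it, since K/L costs almost nothing even when it is uninformative.

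**Conclusion.** The point holds as a minor, conditional one. The protocol states K/L stratification, the SAP's randomisation section does not, and Section 10.5 leaves K/L unstated in the analysis that decides success. If the term is truly absent, the study gives up about 0.5-5% of the standard error. No conclusion is threatened at the Month 24 difference; the gain would be felt only if the Month 60 difference shrank towards the 11-14 point range.

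The size rests on the assumed R² of 1-10%, an even K/L split, and assumed within-subject correlation and baseline effect. The simulation treated the covariance as known, whereas 10.5 plans an unstructured matrix for the MMRM, and it did not include baseline imputation for treatment failures. The direction (a little precision, no bias) does not depend on these choices. Confidence is medium because the pivotal model could not be read.

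**What to change.** 1. Reconcile Protocol 5.11, 7.3.2 and 10.1 with SAP Section 6 on whether K/L was a randomisation factor.
2. List every term of the primary PROC BGLIMM model in 10.5. If the pivotal model already contains K/L, say so and change nothing else.
3. If it does not, add K/L stratum and K/L-by-visit as fixed effects to the primary model and the supporting MMRM, under the diffuse normal priors that 10.5 already gives fixed effects. Do this by dated amendment before any Month 60 result is analysed or posted, including through the interim reports of Section 11 (October 2022, 2023 and 2024). Report the unchanged pivotal model alongside.
4. If Month 60 results have already been posted, keep the pivotal model as primary and make the K/L-adjusted model a prespecified supportive analysis.
5. Use site at most as a random intercept with a stated diffuse prior in a sensitivity analysis.

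The cost is an amendment and a few lines of code; K/L is already read off-site at screening. The real downside is that the primary model would no longer be identical to the pivotal one, and the change would be made with Month 24 results known. Limiting the addition to K/L, dating it and showing both models keeps that criticism manageable.

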## 10.6 Statistical Analyses

### 10.6.1 Overview

The data will be summarized in tables listing the mean, standard deviation or standard error, median, minimum, maximum, and number of subjects in a group for continuous data (e.g. age, weight) or in tables listing count and percentage for categorical data (e.g. gender, previous surgical treatment). Data will be presented by visit and treatment arm. Data listings by subject will be provided. The effects of noncompliance, dropouts, and covariates, and their interactions with treatment will be assessed to determine the impact on the general applicability of results from this study.

Primary and confirmatory secondary analyses will be conducted in the FAS. All efficacy endpoints will be tested on the FAS analysis set as well. Safety analyses will be conducted on the safety analysis set composed of all treated subjects.

Deviations from the current statistical considerations, should there be any, will be described in an amendment to the protocol and/or the statistical analysis plan (SAP). Any such deviations will be justified and described in the final report as appropriate.

### 10.6.2 Subject Disposition

Subject disposition will be tabulated; the number of enrolled, treated, prematurely terminated, and completed subjects will be summarized separately according to treatment and by visit (where relevant). A list of dropouts will be prepared including treatment, reason for discontinuation and time of discontinuation.

## 10.7 Efficacy

### 10.7.1 Primary Endpoint Analysis

The primary endpoint analysis is described above in section 10.5. Statistical power for testing the primary efficacy hypothesis was approximated as follows. In the FAS, the mean

A Post Approval Multicenter Open-label

Randomized Controlled Trial of Agili-C™ vs.

Surgical Standard of Care (SSOC) for the  
Treatment of Joint Surface Lesions of the Knee

CLN0021-US

Rev. 8

March 29, 2022

(SD, N) improvement was 43.0 (20.1, N=160) and 20.5 (20.9, N=79) among subjects treated with Agili-C and SSOC, respectively, or a group difference of 22.5. Since this is a 5-year study, for the purpose of sample size justification, it was assumed that the sample sizes would be 75% as large, or 120 and 59, respectively. It was further assumed that the SD would be 20% higher than the maximum of 20.1 and 20.9 or 25. Under these assumptions, statistical power based on a pooled t-test with 1-sided type 1 error rate of  $\alpha=0.025$ , is 99%. If the mean improvement at 5 years is only 80% as large as observed at Month 24 for Agili-C, i.e., 34.4, or a group difference of only 13.9, then statistical power is 93.5%. Under these assumptions, as long as the group difference in mean improvements from baseline to Month 60 is at least as large as 11.2, then power is at least 80%. Further, these computations are conservative since the statistical modelling will include information for subjects up to the point of loss-to-follow-up. Therefore, statistical power appears adequate for confirming Month 60 superiority given the results from Month 24 and reasonably conservative assumptions.

### **10.7.2 Secondary Confirmatory Endpoint Analyses**

This trial has 6 confirmatory secondary endpoints that will be tested hierarchically in the order presented below to preserve overall Type I Error = 0.05. The following confirmatory hypotheses will be tested similarly to the primary endpoint as described in the preceding section:

#### Confirmatory I

$H_0$ : Change in KOOS QOL (Agili-C™) at 60M  $\leq$  Change in KOOS QOL (SSOC) at 60M

$H_1$ : Change in KOOS QOL (Agili-C™) at 60M  $>$  Change in KOOS QOL (SSOC) at 60M

#### Confirmatory II

$H_0$ : Change in KOOS Pain (Agili-C™) at 60M  $\leq$  Change in KOOS Pain (SSOC) at 60M

$H_1$ : Change in KOOS Pain (Agili-C™) at 60M  $>$  Change in KOOS Pain (SSOC) at 60M

CLN0021-US-Investigational Plan		Document Number: CLN-0000002
 CartiHeal		Document Version: 8.0 Effective Date: 08-Jun-2022 (GMT+2) Page 53 of 80
A Post Approval Multicenter Open-label Randomized Controlled Trial of Agili-C™ vs. Surgical Standard of Care (SSOC) for the Treatment of Joint Surface Lesions of the Knee		CLN0021-US Rev. 8 March 29, 2022

### Confirmatory III

$H_0$ : Change in KOOS ADL (Agili-C™) at 60M  $\leq$  Change in KOOS ADL (SSOC) at 60M

$H_1$ : Change in KOOS ADL (Agili-C™) at 60M  $>$  Change in KOOS ADL (SSOC) at 60M

### Confirmatory IV

$H_0$ : Change in KOOS Symptoms (Agili-C™) at 60M  $\leq$  Change in KOOS Symptoms (SSOC) at 60M

$H_1$ : Change in KOOS Symptoms (Agili-C™) at 60M  $>$  Change in KOOS Symptoms (SSOC) at 60M

### Confirmatory V

$H_0$ : Change in KOOS Sports (Agili-C™) at 60M  $\leq$  Change in KOOS Sports (SSOC) at 60M

$H_1$ : Change in KOOS Sports (Agili-C™) at 60M  $>$  Change in KOOS Sports (SSOC) at 60M

### Confirmatory VI

$H_0$ : Response Rate (Agili-C™) at 60M  $\leq$  Response Rate (SSOC) at 60M

$H_1$ : Response Rate (Agili-C™) at 60M  $>$  Response Rate (SSOC) at 60M

#### **10.7.3 Definition of Overall KOOS Responder Rate**

- a. *Response = increase from baseline to 60 months of  $\geq 30$  points on overall KOOS*
- b. *Non-response = otherwise.*

*Type I error will be controlled hierarchically, such that testing will be done on each endpoint only if the null has been rejected for all preceding endpoints.*

#### **10.7.4 Secondary Endpoint Analysis**

Secondary analysis will repeat the primary and confirmatory efficacy analyses in the FAS population. The FAS and PP differ by one Agili-C subjects. Therefore, these analysis are

## A Post Approval Multicenter Open-label

## Randomized Controlled Trial of Agili-C™ vs.

Surgical Standard of Care (SSOC) for the  
Treatment of Joint Surface Lesions of the Knee

CLN0021-US

Rev. 8

March 29, 2022

nearly identical and so additional secondary endpoints will only be tested in FAS in order to reduce the number of statistical tests performed.

- Change from baseline in average overall KOOS score (Pain, Symptoms, QOL, ADL & Sports) at 36 and 48 Months
- Change from baseline in IKDC Subjective Knee Evaluation at 36, 48 and 60 Months
- Change from baseline in Tegner score at 36, 48 and 60 Months
- Change from baseline QOL as measured by SF-12 v2 at 36, 48 and 60 Months
- Change from baseline to 36, 48 and 60 months in the average overall KOOS score (Pain, Symptoms, QOL, ADL & Sports) in patients with chondral lesions
- Change from baseline to 60 months in the average overall KOOS score (Pain, Symptoms, QOL, ADL & Sports) in patients with osteochondral lesions
- Change from baseline to 36, 48 and 60 months in the average overall KOOS score (Pain, Symptoms, QOL, ADL & Sports) in patients with single lesion
- Change from baseline to 36, 48 and 60 months in the average overall KOOS score (Pain, Symptoms, QOL, ADL & Sports) in patients with multiple lesions
- Change from baseline to 36, 48 and 60 months in the average overall KOOS score (Pain, Symptoms, QOL, ADL & Sports) in patients without osteoarthritis (K/L 0-1)
- Change from baseline to 36, 48 and 60 months in the average overall KOOS score (Pain, Symptoms, QOL, ADL & Sports) in patients with osteoarthritis (K/L 2-3)
- Change from baseline to 36, 48 and 60 months in the average overall KOOS score (Pain, Symptoms, QOL, ADL & Sports) in patients with total lesion(s) size  $\leq 3\text{cm}^2$
- Change from baseline to 36, 48 and 60 months in the average overall KOOS score (Pain, Symptoms, QOL, ADL & Sports) in patients with total lesion(s) size  $> 3\text{cm}^2$
- Change from baseline to 36, 48 and 60 months in the average overall KOOS score (Pain, Symptoms, QOL, ADL & Sports) in patients with previous ligament reconstruction
- Change from baseline to 36, 48 and 60 months in the average overall KOOS score (Pain, Symptoms, QOL, ADL & Sports) in patients without previous ligament reconstruction
- Change from baseline to 36, 48 and 60 months in the average overall KOOS score (Pain, Symptoms, QOL, ADL & Sports) in patients with intact meniscus

	CLN0021-US-Investigational Plan A Post Approval Multicenter Open-label Randomized Controlled Trial of Agili-C™ vs. Surgical Standard of Care (SSOC) for the Treatment of Joint Surface Lesions of the Knee	Document Number: CLN-0000002 Document Version: 8.0 Effective Date: 08-Jun-2022 (GMT+2) Page 55 of 80 CLN0021-US Rev. 8 March 29, 2022
--	--	---

- Change from baseline to 36, 48 and 60 months in the average overall KOOS score (Pain, Symptoms, QOL, ADL & Sports) in patients with previous partial meniscectomy
- Change from baseline to 636, 48 and 0 months in the average overall KOOS score (Pain, Symptoms, QOL, ADL & Sports) in patients with concomitant partial meniscectomy
- Change from baseline to 36, 48 and 60 months in the average overall KOOS score (Pain, Symptoms, QOL, ADL & Sports) in active patients
- Change from baseline to 36, 48 and 60 months in the average overall KOOS score (Pain, Symptoms, QOL, ADL & Sports) in non-active patients

